6.2. Secondary Endpoint(s)

6.2.1. Safety Endpoints

Refer to [Section 6.6](#).

6.2.2. Efficacy Endpoints

The following analyses will be based on the FAS by treatment group. Assessment of response will be made using RECIST v1.1.

6.2.2.1. Objective Response as Assessed by the Investigator per RECIST v1.1

The following analyses will be based on the FAS by treatment group. Assessment of response will be made using RECIST v1.1.

Best Overall Response (BOR) will be assessed based on reported overall lesion responses at different evaluation time points from the first dose of study treatment until the first documentation of PD, according to the following rules:

- CR = at least two determinations of CR at least 4 weeks apart and before first documentation of PD.
- PR = at least two determinations of PR or better at least 4 weeks apart and before first documentation of PD (and not qualifying for a CR).
- SD (applicable only to patients with measurable disease at baseline) = at least one SD assessment (or better) ≥ 6 weeks after the first dose of study treatment and before first documentation of PD (and not qualifying for CR or PR).
- Non-CR/non-PD (applicable only to patients with non-measurable disease at baseline) = at least one non-CR/non-PD assessment (or better) ≥ 6 weeks after the first dose of study treatment and before first documentation of PD (and not qualifying for CR or PR).

- PD = progression \leq 12 weeks after the first dose of study treatment (and not qualifying for CR, PR, SD or non-CR/non-PD).
- NE: all other cases.

Only tumor assessments performed on or before the start of any further anti-cancer therapies will be considered in the assessment of BOR. Clinical deterioration will not be considered as documentation of disease progression.

Objective Response (OR) is defined as BOR of CR or PR according to RECIST v1.1

Patients who do not have a post-baseline radiographic tumor assessment (including due to early clinical progression), who receive anti-cancer therapies other than the study treatments prior to reaching a CR or PR, or who die, progress, or drop out for any reason prior to reaching a CR or PR will be counted as non-responders in the assessment of OR. Each patient will have an objective response status (0: no OR; 1: OR). OR rate (ORR) is the proportion of patients with OR in the analysis set.

ORR by treatment group will also be calculated along with the 2-sided 95% CI using the Clopper-Pearson method (exact CI for a binomial proportion as computed by default by the FREQ procedure using the EXACT option).

In addition, the frequency (number and percentage) of patients with BOR of CR, PR, SD, non-CR/non-PD (applicable only to patients with non-measurable disease at baseline), PD and NE will be tabulated. Patients with BOR of NE will be summarized by reason for having NE status. The following reasons will be used:

- Inadequate baseline assessment (includes missing assessment or non-measurable disease at baseline).
- No post-baseline assessments due to death.
- No post-baseline assessments due to other reasons.
- All post-baseline assessments have overall response NE.
- New anti-cancer therapy started before first post-baseline assessment.
- SD of insufficient duration (<6 weeks after the first dose of study treatment).
- PD too late (>12 weeks after the first dose of study treatment).

Special and rare cases where BOR is NE due to both early SD and late PD will be classified as 'SD too early'.

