6.2.2.5. Progression-free Survival (Expansion Cohort Only)

Progression-Free Survival (PFS) is defined as the time from the first dose of study treatment to the date of the first documentation of PD or death due to any cause, whichever occurs first. PFS data will be censored on the date of the last adequate tumor assessment for patients who do not have an event (PD or death), or for patients with an event after two or more missing tumor assessments. For patients who start a new anti-cancer therapy prior to an event, PFS data will be censored on the date of the last adequate tumor assessment prior to starting the new anti-cancer therapy. Patients who do not have an adequate baseline tumor assessment or who do not have an adequate post-baseline tumor assessment will be censored on the first dose of study treatment unless death occurred on or before the time of the second planned tumor assessment in which case the death will be considered an event ([Table 3](#)).

In this study antitumor activity will be assessed through radiological tumor assessments conducted at baseline, on treatment every 8 weeks up to 1 year, then every 3 months and whenever disease progression is suspected (eg, symptomatic deterioration). Assessments will be repeated at EOT only if not done in the previous 8 weeks. The allowable time window for disease assessments is ± 7 days while on treatment and whenever disease progression is suspected (eg, symptomatic deterioration).

The censoring and event date options to be considered for the PFS and DR analysis are presented in [Table 3](#).

$$\text{PFS (months)} = [\text{date of event or censoring} - \text{first dose of study treatment} + 1] / 30.4375$$

Table 3. Outcome and Event Dates for PFS and DR Analyses

Scenario	Date of event/censoring	Outcome
No adequate baseline assessment	first dose of study treatment ^a	Censored ^a
PD or death 
 - After at most one missing or inadequate post-baseline tumor assessment, OR - ≤ 16 weeks after the first dose of study treatment 	Date of PD or death	Event
PD or death after 2 or more missing or inadequate post-baseline tumor assessments	Date of last adequate tumor assessment ^b documenting no PD before new anti-cancer therapy is given or missed tumor assessments	Censored
No PD and no death	Date of last adequate tumor assessment ^b documenting no PD before new anti-cancer therapy is given or missed tumor assessments	Censored

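### The RECIST best overall response rule stops counting PD at 12 weeks, between two 8-weekly scans, so PD at an on-schedule second scan with no adequate first scan is reported as not evaluable

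*SAP*

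**What the plan says.** **BOR (SAP 6.2.2.1).** PD is assigned only when progression occurs no later than "12 weeks after the first dose of study treatment (and not qualifying for CR, PR, SD or non-CR/non-PD"). The residual category is "NE: all other cases". The list of reasons for NE includes "PD too late (>12 weeks after the first dose of study treatment"). SD needs an assessment of SD or better at 6 weeks or later and before PD. BOR is tabulated on the full analysis set by treatment group, so the rule applies to dose-finding and expansion patients alike.

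**Scan calendar (SAP 6.2.2.5; the same schedule is in Protocol 3.1.5 and 7.2).** Tumour assessments are done "on treatment every 8 weeks up to 1 year, then every 3 months and whenever disease progression is suspected". On the tolerance: "The allowable time window for disease assessments is ± 7 days while on treatment".

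**PFS (SAP 6.2.2.5, Table 3; expansion cohorts only).** PD or death counts as an event under either of two alternatives. The first is "After at most one missing or inadequate post-baseline tumor assessment, OR"; the second is an event no later than "16 weeks after the first dose of study treatment".

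**irRECIST BOR (SAP 6.3.1).** irPD has to be confirmed, but it carries no upper time limit.

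**The concern.** A time limit on PD as best response serves to exclude progression found only after a long stretch without evaluable scans. For that, it has to be set against the trial's own scan calendar. Twelve weeks matches no planned scan here: it falls after the first window has closed and before the second has opened. One missed or unreadable first scan is then enough to turn a documented, on-schedule progression into a not-evaluable result.

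At stake is the accuracy of the PD and NE rows of the BOR table. In the expansion cohorts there is also a visible inconsistency: one radiological finding is accepted as progression for PFS and treated as not evaluable for BOR.

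**Working it through.** **Inputs.** Scan interval 8 weeks and window 7 days either way (SAP 6.2.2.5); BOR limit for PD 12 weeks and SD minimum 6 weeks (SAP 6.2.2.1); PFS alternatives, at most one missing or inadequate scan, or 16 weeks (SAP Table 3); 1 week = 7 days (SAP 5.2.8). Days below are days elapsed since first dose.

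**The plan's own figure.** The text of SAP 6.2.2.5 allows an early death to count as an event up to the second planned assessment. 2 × 8 weeks = 16 weeks = day 112, which agrees with Table 3.

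**Scan windows.**
- First scan: 56 ± 7 = days 49-63 (weeks 7-9).
- Second scan: 112 ± 7 = days 105-119 (weeks 15-17).
- BOR limit: 12 × 7 = day 84. Since 63 < 84 < 105, it lies in the gap.

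**Applying both rules to the first documented PD.**

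| PD found at | Day | BOR as written (limit day 84) | PFS, expansion cohorts | BOR if limit is 16 weeks (day 112) | BOR if limit is 17 weeks (day 119) |
|---|---|---|---|---|---|
| First scan | 49, 56, 63 | PD | event | PD | PD |
| Second scan, first missed or NE | 105 | NE | event | PD | PD |
| Second scan, first missed or NE | 112 | NE | event | PD | PD |
| Second scan, first missed or NE | 119 | NE | event | NE | PD |

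Day 105 is already past day 84, so BOR is NE on every day of the second window. PFS is an event on every day of that window because only one assessment is missing or inadequate. The 16-week alternative also applies up to day 112 but is not needed.

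**When the problem does not arise.** The earliest in-window first scan is day 49, beyond the 6-week SD minimum (day 42). Any in-window first scan read as SD or better therefore gives a BOR of at least SD, and there is no conflict.

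**Size.** One reclassified patient shifts the PD/NE split by 1/40 = 2.5 percentage points in a group of 40, or 1/6 = 16.7 points in a group of 6. The documents give no rate of missed or NE first scans. Assume 5-10% lack an adequate first scan and 30-70% of those have PD at the second:
- low: 40 × 0.05 × 0.30 = 0.6 patients
- high: 40 × 0.10 × 0.70 = 2.8 patients
- ceiling, if all of them progress at the second scan: 40 × 0.05 = 2 to 40 × 0.10 = 4 patients

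**The case against.** The strongest reply is that the rule is explicit and its effect is disclosed. Late PD has its own NE reason, so a reader can add that row back to PD, and Protocol 9.4 lists response at each visit and the progression date by patient. That stands as mitigation. It does not make the tabulated PD and NE rows right for a patient who was scanned on schedule.

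Second, BOR and PFS are different quantities, and nothing in either document requires a shared cut-off. That is also true, and the point does not depend on it: the 12-week limit already fails against the scan calendar, and the disagreement with PFS is a consequence.

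Third, 12 weeks covers the first scan plus three further weeks (week 9 to week 12), and scans are also required when progression is suspected. This limits how many patients are affected. It does not help a patient whose first adequate scan is the second planned one.

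A reader might infer that the fault is a clash between the 12 weeks of BOR and the 16 weeks of Table 3, with 16 weeks serving as the limit for one missed scan. Table 3 does not support this. Its two conditions are alternatives, the first has no week limit, and it alone makes PD at week 17 after one missed scan an event.

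**Conclusion.** The rule is wrong as written for this scan schedule, and the consequence is minor. PD at an in-window second scan can never be a BOR of PD when there is no adequate first scan. The misfit applies to all cohorts; the disagreement with PFS applies only to the expansion cohorts.

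The case requires an adequate baseline, no qualifying assessment of SD or better, no PD documented by week 12, and no new anti-cancer therapy before the PD scan. Under the assumed rates it concerns about 0.6 to 2.8 of 40 patients, and 40 is itself the maximum expansion total.

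Three stronger readings are not supported:
- **That 2 to 4 of 40 patients would be misclassified.** This is an upper bound, because it takes every patient without an adequate first scan to have PD at the second.
- **That the response rate or a decision is affected.** PD and NE are both non-response, so ORR is unchanged. MTD rests on DLTs, the PFS rules are untouched, and no hypothesis test is planned (SAP 5.1.1).
- **That the documents show 12 weeks to be either an oversight or a deliberate choice.** Neither document gives a reason for the figure.

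**What to change.** In SAP 6.2.2.1, change the limit for PD as BOR from 12 weeks to 17 weeks after first dose (second planned scan at 16 weeks plus the 7-day window), and change the matching late-PD reason for NE to more than 17 weeks. A bare 16 weeks would leave in-window scans on days 113-119 as NE.

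The change makes BOR agree with PFS for PD at an in-window second scan. It does not align the two everywhere: PD at a second scan taken after the window, for example at week 18 after one missed scan, would still be NE for BOR and an event for PFS. If the sponsor prefers to keep 12 weeks, the SAP should say why such PD is not evaluable for BOR.

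The cost is one number in two places, with no new data collection and no change to any other analysis.

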6.2.2.2. Tumor Shrinkage from Baseline

Tumor shrinkage will be summarized as the percent change from baseline in target lesions (sum of longest diameter for non-nodal lesion and short axis for nodal lesion) per time point. It will be derived as:

- $((\text{Sum of target lesions at week XX} - \text{sum of target lesions at baseline}) / \text{sum of target lesions at baseline}) \times 100$.

The maximum reduction in target lesions from baseline will be derived across all the post-baseline assessments until documented disease progression, excluding assessments after start of subsequent anti-cancer therapy, as:

- Minimum of $((\text{sum of target lesions at week XX} - \text{sum of target lesions at baseline}) / \text{sum of target lesions at baseline}) \times 100$.

A waterfall plot of maximum percent reduction in the sum of longest diameter for non-nodal lesions and short axis for nodal lesions from baseline will be created. This plot will display the best percentage change from baseline in the sum of the diameter of all target lesions for each patient with measurable disease at baseline and at least one post-baseline assessment.

6.2.2.3. Duration of Response

Duration of Response (DR) is defined, for patients with OR, as the time from the first documentation of objective response (CR or PR) to the date of first documentation of PD or death due to any cause. If a patient has not had an event (PD or death), DR is censored at the date of last adequate tumor assessment. The censoring rules for DR are as described below for PFS in [Table 3](#).

$$\text{DR (months)} = [\text{date of event or censoring} - \text{first date of OR} + 1] / 30.4375$$

Kaplan-Meier estimates (product-limit estimates) will be presented by treatment group together with a summary of associated statistics including the median DR time with 2-sided 95% CIs. In particular, the DR rate at 3, 6 and 12 months will be estimated with corresponding 2-sided 95% CIs. The CIs for the median will be calculated according to Brookmeyer and Crowley and the CIs for the survival function estimates at the time points defined above will be derived using the log-log transformation according to Kalbfleisch and Prentice (conftype=loglog default option in SAS Proc LIFETEST) with back transformation to a CI on the untransformed scale. The estimate of the standard error will be computed using Greenwood's formula.

DR will be displayed graphically and analyzed using Kaplan-Meier methodology. If the number of patients with OR is small, the Kaplan-Meier method may not provide reliable estimates. In this case, only descriptive statistics or listings will be provided.

6.2.2.4. Time to Response

Time to response (TTR) is defined, for patients with OR, as the time from the first dose of study treatment to the first documentation of objective response (CR or PR) which is subsequently confirmed.

$$\text{TTR (in months)} = [\text{first date of OR} - \text{first dose of study treatment} + 1] / 30.4375$$

TTR will be summarized using simple descriptive statistics (mean, SD, median, min, max, Q1, Q3).

6.2.2.5. Progression-free Survival (Expansion Cohort Only)

Progression-Free Survival (PFS) is defined as the time from the first dose of study treatment to the date of the first documentation of PD or death due to any cause, whichever occurs first. PFS data will be censored on the date of the last adequate tumor assessment for patients who do not have an event (PD or death), or for patients with an event after two or more missing tumor assessments. For patients who start a new anti-cancer therapy prior to an event, PFS data will be censored on the date of the last adequate tumor assessment prior to starting the new anti-cancer therapy. Patients who do not have an adequate baseline tumor assessment or who do not have an adequate post-baseline tumor assessment will be censored on the first dose of study treatment unless death occurred on or before the time of the second planned tumor assessment in which case the death will be considered an event ([Table 3](#)).

In this study antitumor activity will be assessed through radiological tumor assessments conducted at baseline, on treatment every 8 weeks up to 1 year, then every 3 months and whenever disease progression is suspected (eg, symptomatic deterioration). Assessments will be repeated at EOT only if not done in the previous 8 weeks. The allowable time window for disease assessments is ± 7 days while on treatment and whenever disease progression is suspected (eg, symptomatic deterioration).

The censoring and event date options to be considered for the PFS and DR analysis are presented in [Table 3](#).

$$\text{PFS (months)} = [\text{date of event or censoring} - \text{first dose of study treatment} + 1] / 30.4375$$

Table 3. Outcome and Event Dates for PFS and DR Analyses

Scenario	Date of event/censoring	Outcome
No adequate baseline assessment	first dose of study treatment ^a	Censored ^a
PD or death 
 - After at most one missing or inadequate post-baseline tumor assessment, OR - ≤ 16 weeks after the first dose of study treatment 	Date of PD or death	Event
PD or death after 2 or more missing or inadequate post-baseline tumor assessments	Date of last adequate tumor assessment ^b documenting no PD before new anti-cancer therapy is given or missed tumor assessments	Censored
No PD and no death	Date of last adequate tumor assessment ^b documenting no PD before new anti-cancer therapy is given or missed tumor assessments	Censored
Treatment discontinuation due to 'Disease progression' without documented progression	Not applicable	Information is ignored. Outcome is derived based on documented progression only.
New anti-cancer therapy given	Date of last adequate tumor assessment ^b documenting no PD before new anti-cancer therapy is given or missed tumor assessments	Censored

^a However if the patient dies ≤ 16 weeks after the first dose of study treatment the death is an event with date on death date.

^b If there are no adequate post-baseline assessments prior to PD or death, then the time without adequate assessment should be measured from the first dose of study treatment; if the criteria were met the censoring will be on the 'start date.'

Kaplan-Meier estimates (product-limit estimates) will be presented by treatment group together with a summary of associated statistics including the median PFS time with 2-sided 95% CIs. In particular, the PFS rate at 3, 6, 9, 12 and 15 months will be estimated with corresponding 2-sided 95% CIs. The CIs for the median will be calculated according to Brookmeyer and Crowley and the CIs for the survival function estimates at the time points defined above will be derived using the log-log transformation according to Kalbfleisch and Prentice (conftype=loglog default option in SAS Proc LIFETEST) with back transformation to a CI on the untransformed scale. The estimate of the standard error will be computed using Greenwood's formula.

Frequency (number and percentage) of patients with each event type (PD or death) and censoring reasons will be presented by treatment group. Reasons for censoring will be summarized according to the categories in [Table 4](#) following the hierarchy shown.

Table 4. PFS Censoring Reasons and Hierarchy

Hierarchy	Condition	Censoring Reason
1	No adequate baseline assessment	No adequate baseline assessment
2	Start of new anti-cancer therapy.	Start of new anti-cancer therapy
3	Event after 2 or more missing or inadequate post-baseline tumor assessments/ first dose of study treatment	Event after missing assessments ^a
4	No event and End of study (EOS) = Subject refused further follow-up	Withdrawal of consent
5	No event and lost to follow-up in any disposition page	Lost to follow-up
6	No event and EOS present and no adequate post-baseline tumor assessment	No adequate post-baseline tumor assessment
7	No event and none of the conditions in the prior hierarchy are met	Ongoing without an event

^a 2 or more missing or inadequate post-baseline tumor assessments.

The PFS time or censoring time and the reasons for censoring will also be presented in a patient listing.

Time of Follow-Up for PFS

A plot will be generated to compare planned and actual relative day of tumor assessments by treatment group. A Kaplan-Meier plot for PFS follow-up duration will also be generated to assess the follow-up time in the treatment groups reversing the PFS censoring and event indicators.

6.2.3. Pharmacokinetic endpoints

The following pharmacokinetic analyses will be conducted by treatment group.

PF-05082566 and Mogamulizumab PK Concentrations:

Descriptive statistics (n, mean, SD, %CV, median, minimum, maximum, and the number of concentrations above the lower limit of quantification) of serum PK concentrations for PF-05082566 and mogamulizumab will be presented in tabular form by nominal visit, cycle, dose and nominal time.

Linear and semi-log plots of median serum concentrations vs nominal time will be prepared for Cycle 5 by dose (all doses on the same plot). Similar plots will be prepared for each individual patient's serum concentrations by dose (all subjects on the same plot).

PF-05082566 and Mogamulizumab PK Parameters:

The PF-05082566 and mogamulizumab PK parameters detailed in [Section 3.2.3](#) for Cycle 5 will be listed and summarized by dose using descriptive statistics as specified in [Table 5](#). PK parameters with zero values will be excluded from the calculation of geometric means and geometric %CV.

Table 5. Summary Statistics of PK Parameters

Parameter	Summary Statistics
AUC _{last} , AUC _{tau} , C _{max} , C _{trough} , CL, V _{ss} , AUC _{0-last(dn)} , AUC _{tau(dn)} , C _{max(dn)}	N, arithmetic mean, median, cv%, standard deviation, minimum, maximum, geometric mean and geometric cv%.
T _{max}	N, median, minimum, maximum.
t _{1/2}	N, arithmetic mean, median, cv%, standard deviation, minimum, maximum.

[figure not shown]
Dose normalized AUC_{tau} and C_{max} for PF-05082566 may be plotted against dose (using a logarithmic scale). These plots will include individual patient values and the geometric means for each dose and will be used to help understand the dose proportionality for PF-05082566.

6.2.4. Population Pharmacokinetic Endpoints

Pharmacokinetic and pharmacodynamic data from this study may be analyzed using modeling approaches and may also be pooled with data from other studies to investigate any association between PF-05082566 and mogamulizumab exposure and biomarkers or significant safety/efficacy endpoints. The results of these analyses, if performed, may be reported separately.

